During the manufacturing process of AdCh63 ME-TRAP a biocide named Kathon will be used. Kathon is added to body washes, conditioners, liquid soaps, shampoos and wipes as a preservative. The maximum dose is 0.1% for 'rinse off' products and for 'leave on' products it is 0.05%. It has been approved by regulatory authorities throughout the world as a preservative in these products. As a skin sensitiser it is known to cause contact dermatitis. An internal study SOP/P22 was set up by Clinical Biomanufacturing Facility (CBF) to quantify the levels of Kathon that were removed during the final purification step of buffer exchange during the manufacture of the vaccine. This study utilized high performance liquid chromatography and showed that trace amounts of Kathon may be left on the desalting column after carrying out the rinse and sanitisation steps. However, the study confirmed greater than 99.9975% removal

of Kathon to approximately 30 fold less than the limits for 'leave on' products containing Kathon. We will exclude anyone from the study with a history of clinically significant contact dermatitis or sensitivity to Kathon.

HDCRV

Mild and self-limited local reactions such as pain at the site of injection, redness and swelling occur in 21–74% of vaccinees. Bleomicin and neomycin are used in the manufacturing process and therefore volunteers with a history of hypersensitivity to these drugs, or aminoglycoside antibiotics, will be excluded from the trial.

Systemic Reactions

A proportion of volunteers may report a transient mild 'flu-like illness within 24 hours of vaccination which resolves rapidly.

MVA ME-TRAP

Systemic effects can occur with MVA ME-TRAP and are dose related, with symptoms occurring at a higher frequency and greater intensity in volunteers receiving higher doses. At higher doses $(1.5 - 2 \times 10^8 \text{ pfu})$ the majority of subjects experience a mild flu-like illness (symptoms of malaise (up to 87.5%), myalgia (up to 75%) and feverishness (up to 75%) after the first dose of MVA ME-TRAP that is short-lived (12 to 24 hours). This occurs within 24 hours of vaccination and is less frequent with lower doses (<15% of immunisations) and second or third MVA immunisations. Objective fever occurs in up to 37.5% of vaccinees.

AdCh63 ME-TRAP

Similar mild 'flu-like symptoms can occur with AdCh63 ME-TRAP. These symptoms occur in 28/39 of volunteers at 5 x 10^{10} vp intramuscularly. The frequency of 'flu-like symptoms increases with use of the 2 x 10^{11} vp dose to 9/10. Objective fever has not been observed in 46 males in Africa, and has occurred in 26/85 volunteers in the UK (at doses up to 2 x 10^{11} vp).

HDCRV

Mild systemic reactions such as fever, headache, dizziness and gastrointestinal symptoms occur in 5–40%, and systemic hypersensitivity following booster injections in 6% of vaccinees, but are less common following primary immunization.

With any vaccine, serious allergic reactions including anaphylaxis may occur. The exact risk of anaphylaxis is difficult to quantify, and is estimated at approximately 1 in 10^5 to 10^6 . Volunteers will be vaccinated in a clinical area where Advanced Life Support drugs and equipment are immediately available for the management of serious adverse reactions.

Prophylactic use of paracetamol or non-steroidal anti-inflammatory drugs is not required. Parents of study subjects will be provided with paracetamol and they will be advised to use this drug to treat local or systemic adverse events as they see fit should these develop post-immunisation, but not prophylactically.

2.3.2. Known Potential Benefits

There are no known benefits to volunteers for participation in this phase I study. All children enrolled will receive a full course of rabies vaccine (HDCRV) at the end of the trial, this will be arranged by the PI, [name].

3. OBJECTIVES

3.1. Primary Objective

To assess the safety of a heterologous prime-boost vaccine strategy with AdCh63 ME-TRAP and MVA ME-TRAP in healthy adults and children in The Gambia.

3.2. Secondary Objectives

To assess the immunogenicity of a heterologous prime-boost vaccine strategy with AdCh63 ME-TRAP and MVA ME-TRAP in healthy adults and children in The Gambia.

3.3 Tertiary Objective

To compare the immunogenicity of two doses of MVA ME-TRAP in children.

4. STUDY DESIGN

4.1. Description and Justification of Study Design

This is a single-blinded controlled dose escalation phase I study. The trial period will be approximately 12 months.

The sample size for phase I studies balances the need to avoid exposing a large group to an unknown risk with the need for data from an adequate sample. The aim is not to provide pre-marketing safety data but to justify the future study of larger groups. The sample size was determined by the requirement to make a preliminary evaluation of inter-group variability to avoid excessive risk. Further justification of the study design is contained in Section 2.2. The addition of a control group to the groups involving children aged 2-6 (Groups 2 and 3) is to control for the anticipated high frequency of concurrent diseases in this population and aid in the objective assessment of the relationship of adverse events to vaccination. There may be benefit to the malaria vaccinated volunteers in terms of reduced susceptibility to malaria although this trial is not designed to assess this possibility, and there is no evidence that this is the case in this population at present since the vaccine has not been tested. A comparator vaccine, rather than saline placebo will be used for the control groups. The comparator vaccine will be the HDCRV. Although this will be administered in a 0, 2 month regimen, there is evidence from the SPC that two vaccines may be immunogenic and may provide some efficacy against rabies. To avoid potential inequality, all volunteers will receive a full standard schedule of HDCRV at the end of the trial.

The control group volunteers will also undergo venesection for safety laboratory testing, and will undergo ex-vivo ELISPOT immunology analysis exactly as planned for the vaccinated volunteers, to control for TRAP-specific T cell responses which may develop during the study period as a result of natural exposure to *P.falciparum*.

Allocation bias will be reduced by randomised allocation to study groups. In addition, single-blinding will be employed to reduce bias in reporting of adverse events. Given that the crucial safety assessment for these viral vectored vaccines occurs in the first 72 hours (when the majority of vaccine-related adverse events are

reported) the fieldworkers conducting the early safety assessments during this period will be blinded to vaccine allocation, as will the volunteer and their carer. Should the fieldworker have a significant safety concern the trial clinician (who will not be blinded to group allocation) will review the volunteer.

4.2. Study groups

Study groups are as follows: (All injections are administered by the intramuscular route – IM).

Group 1A (6 healthy male volunteers aged 18-50 years): AdCh63 ME-TRAP 1 x 10^{10} vp IM followed by MVA ME-TRAP 2 x 10^{8} pfu IM 8 weeks later

Group 1B (10 healthy male volunteers aged 18-50 years): AdCh63 ME-TRAP 5 x 10¹⁰ vp IM followed by MVA ME-TRAP 2 x 10⁸ pfu IM 8 weeks later

Group 2A (6 healthy children aged 2-6 years): AdCh63 ME-TRAP 1×10^{10} vp IM followed by MVA ME-TRAP 1×10^{8} pfu IM 8 weeks later

Group 2B (6 healthy children aged 2-6 years): AdCh63 ME-TRAP 1 x 10¹⁰vp IM followed by MVA ME-TRAP 2 x 10⁸ pfu IM 8 weeks later

Group 2C (6 healthy children aged 2-6 years): Control HDCRV 1ml IM followed by HDCRV 1ml IM 8 weeks later

Group 3A (6 healthy children aged 2-6 years): AdCh63 ME-TRAP 5 x 10^{10} vp IM followed by MVA ME-TRAP 1 x 10^{8} pfu IM 8 weeks later

Group 3B (6 healthy children aged 2-6 years): AdCh63 ME-TRAP 5 x 10^{10} vp IM followed by MVA ME-TRAP 2 x 10^{8} pfu IM 8 weeks later

Group 3C (6 healthy children aged 2-6 years): Control HDCRV 1ml IM followed by HDCRV 1ml IM 8 weeks later

Duration of study involvement, clinic visits and blood sampling regimes are identical for all volunteers in each study group. There will be a total of 7 clinic attendances, 7 blood sampling occasions and two vaccination visits for each volunteer. Total blood volume for the study period (300 days from first vaccination for all volunteers) will be 190 mLs for group 1 and 35mls for groups 2 & 3.

4.3. Endpoints

4.3.1. Primary Endpoint

All solicited and unsolicited local and general vaccine-linked adverse events (AEs) including clinically significant laboratory abnormalities.

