1. STUDY SUMMARY

Trial Title	Safety and immunogenicity of a heterologous prime-boost vaccine strategy with AdCh63 ME-TRAP and MVA ME-TRAP in healthy adults and children in a malaria endemic area
Trial Identifier	VAC 041
Clinical phase	
Active ingredients of	Chimpanzee Adenovirus 63 expressing multiple epitopes with thrombospondin-related adhesion
vaccines/products	protein (AdCh63 ME-TRAP)
vaccines, products	
	Modified vaccinia Virus Ankara expressing multiple epitopes with thrombospondin-related
	adhesion protein (MVA ME-TRAP)
	Human diploid cell rabies vaccine (HDCRV)
Finished products	AdCh63 ME-TRAP
·	MVA ME-TRAP
	HDCRV
Dose(s)	AdCh63 ME-TRAP: 1×10^{10} vp and 5×10^{10} vp
(-)	MVA ME-TRAP: 1×10^8 pfu and 2×10^8 pfu
	HDCRV: 1ml
Route(s)	Intramuscular needle injection into deltoid region of arm
Principal Investigator	[name]
· · · · · · · · · · · · · · · · · · ·	
Trial Centre	MRC
	[name]
	The Gambia
	Sukuta Health Centre
	The Gambia
Planned Trial Period	January 2010 until June 2011
Study Duration	12-18 months
Primary Objective	Safety of a heterologous prime-boost vaccine strategy with AdCh63 ME-TRAP and MVA ME-TRAP
, ,	in healthy adults and children in a malaria endemic area.
Secondary Objective	Immunogenicity of a heterologous prime-boost vaccine strategy with AdCh63 ME-TRAP and MVA
	ME-TRAP in healthy adults and children in a malaria endemic area.
Tertiary Objective	Descriptive comparison of immunogenicity of two doses of MVA ME-TRAP in children
Planned Sample Size	16 adults
-	36 children (aged 2-6 years)
Vaccination Schedule	Days 0 and 56
Follow-up duration	10 months from enrolment
Blood Sampling Schedule	Screening, D0, D14, D56, D63, D90, D300
Primary Evaluation	Local and systemic solicited and unsolicited adverse events
Criteria	
Secondary Evaluation	Ex vivo and Cultured ELISPOT,
Criteria	ICS for CD4+ and CD8+ T lymphocytes,
	ELISA for TRAP antibody,
	AdCh63 neutralising antibody
Study Design	Single blinded randomised controlled dose escalation phase I study

Schematic of Study Design:

Group 1	А	6 volunteers	AdCh63 ME-TRAP 1 x 10 ¹⁰ vp	MVA ME-TRAP 2 x 10 ⁸ pfu
(Adult males)	В	10 volunteers	AdCh63 ME-TRAP 5 x 10 ¹⁰ vp	MVA ME-TRAP 2 x 10 ⁸ pfu

Group 2 (Aged 2-6)	А	6 volunteers	AdCh63 ME-TRAP 1 x 10 ¹⁰ vp	MVA ME-TRAP 1 x 10 ⁸ pfu		
	В	6 volunteers	AdCh63 ME-TRAP 1 x 10 ¹⁰ vp	MVA ME-TRAP 2 x 10 ⁸ pfu		
	С	6 volunteers	HDCRV 1ml	HDCRV 1ml		

	А	6 volunteers	AdCh63 ME-TRAP 5 x 10 ¹⁰ vp	MVA ME-TRAP 1 x 10 ⁸ pfu		

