7. BLINDING

For groups 2 and 3, the investigators and the vaccinators will be un-blinded to the group allocations. However, the children's parents/carers and field worker assessing adverse events in the 3 days immediately following vaccination will be blinded to the group allocation.

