11.3.5. Serious Adverse Events

A serious adverse event (experience) or reaction is any untoward medical occurrence that at any dose:

- results in death,
- is life-threatening,

Note: The term "life-threatening" in the definition of "serious" refers to an event in which the patient was at risk of death at the time of the event; it does not refer to an event which hypothetically might have caused death if it were more severe.

- requires inpatient hospitalisation or prolongation of existing hospitalisation,
- results in persistent or significant disability/incapacity, or •
- is a congenital anomaly/birth defect. •

Medical and scientific judgment should be exercised in deciding whether expedited reporting is appropriate in other situations, such as important medical events that may not be immediately life-threatening or result in death or hospitalisation but may jeopardise the patient or may require intervention to prevent one of the other outcomes listed in the definition above. These should also usually be considered serious.

11.3.6. **Collection of Adverse Events**

At each visit vital signs will be documented on the CRF together with local reactions at the injection site. The largest diameter through the injection site of any redness will be recorded in millimetres. The largest diameter through the injection site of local swelling, defined as a more generalized swelling of the deltoid muscle will be recorded in millimetres. Severity of these local findings will be graded using the scale given in Table 2.

Table 2: Grading a) for swelling			
Grade	Diameter [mm]		
0	0		
1	< 20		
2	20 – 50		
3	> 50		

b) for redness		
Grade	Diameter [mm]	
0	0	
1	< 50	
2	50 – 100	
3	> 100	

Study subjects/carers will be asked to indicate the maximum degree of pain they experience at the injection site using a scale ranging from 0 to 3 as described in Table 3.

Grade	Description		
0	No pain at all		
1	Painful on touch, no restriction in movement of arms, able to work, drive, carry heavy objects as normal		
2	Painful when limb is moved		
	(i.e. restriction in range of movement in arm, difficulty in carrying objects)		
3	Severe pain at rest		
	(i.e. unable to use arm due to pain.)		
Limitation of arm movement			
Grade	Description		
0	No limitation (> 180 degrees)		
1	Limitation to < 180 degrees		
2	Limitation to < 90 degrees		
3	Limitation to < 30 degrees		

All local reactions will be considered causally related to the vaccination.

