At each visit subjects will be requested to report local and general side effects they might have experienced since they last were seen. These will only be recorded in the CRF if they occurred up to 30 days post vaccination, unless they meet the criteria for serious adverse event as outlined below. The investigator will assess the severity of the solicited signs and symptoms using the key provided in Tables 4 and 5.

GRADE 0	None	
GRADE 1	Mild: Transient or mild discomfort (< 48 hours); no medical intervention/therapy	
	required	
GRADE 2	Moderate: Mild to moderate limitation in activity - some assistance may be needed; no	
	or minimal medical intervention/therapy required	
GRADE 3	Severe: Marked limitation in activity, some assistance usually required; medical	
	intervention/therapy required.	

Table 4: Intensity of the general adverse events in adults will be assessed	as described.
Table 4: Intensity of the general adverse events in adults will be assessed	as described:

Table 5: Intensity of the general adverse events in children (aged 2-6) will be assessed as described:

Systemic (General)	Grade 1	Grade 2	Grade 3
Fever (axillary temp)	≥38C- ≤39C	≥39C - ≤40C	≥40C
Decreased oral intake	Minimal decrease in oral	Below 50% of normal	No oral intake in
	intake	oral intake in 24 hr	24hr
Vomiting	1 episode in 24hr; no	2-3 episodes in 24 hr	> 3 episodes in 24
	interference with activity	OR some interference	hours OR prevents
		with activity	daily activity
Diarrhea	Unformed stool OR 1-3	Partially liquid stools	Completely liquid
	more stools than	OR 4-6 more stools	stools OR >6 more
	baseline in 24 hr	than baseline in 24hr	stools than baseline
			in 24 hr
Reduced activity	Minimal interference	Below 50% of normal	Prevents daily
	with activity	activity in 24 hr	activity
Unsolicited adverse	Minimal interference	Below 50% of normal	Prevents daily
events	with activity	activity in 24 hr	activity

Activity for the purposes of this assessment will be considered oral intake, sleep and play.

The investigator using the guidelines provided in section 11.3.8. will assess the relationship of the event to the administration of the vaccine. Both severity of the event and its relationship to the vaccine administration will be documented in the CRF if occurring up to 30 days post vaccination for groups 2 and 3, unless it fulfils criteria for a serious adverse event (section 11.3.5).

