11.3.8. Reporting of Adverse Events

Every SAE occurring throughout the trial must be reported by telephone, email or fax to the sponsor, LSM and DSMB by the investigator as soon as (s)he is alerted of it and within one working day, even if the investigator considers that the adverse event is not related to vaccination. The investigator will then complete a SAE report form as soon as possible and within five working days or seven calendar days.

Any relevant information concerning the adverse event that becomes available after the SAE report form has been sent (outcome, precise description of medical history, results of the investigation, copy of hospitalisation report, etc.) will be forwarded to the Sponsor in a timely manner. The anonymity of the subjects shall be respected when forwarding this information.

SAEs that are suspected to be related to the vaccine will be reported to the Ethics Committee within 15 calendar days of the site becoming aware of the event. If the event is fatal or life-threatening, the event will be reported within 7 calendar days.

Suspected unexpected serious adverse reactions (SUSARs) will be reported according to national regulatory guidelines. The sponsor pledges to inform the Authorities of any trial discontinuation and specify the reason for discontinuation.

The causal relationship between the AE and the product will first be evaluated by the investigator with the following scale:

No relationship: No temporal relationship to study product; and Alternate aetiology (clinical state, environmental or other interventions); and Does not follow known pattern of response to study product

Possible relationship: Reasonable temporal relationship to study product; or Event not readily produced by clinical state, environmental or other interventions; or Similar pattern of response to that seen with other vaccines

Probable relationship: Reasonable temporal relationship to study product; and Event not readily produced by clinical state, environment, or other interventions or Known pattern of response seen with other vaccines

Definite relationship: Reasonable temporal relationship to study product; and Event not readily produced by clinical state, environment, or other interventions; and Known pattern of response seen with other vaccines

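### Section 4.3.1 limits the primary endpoint to 'vaccine-linked' adverse events, so in groups 2 and 3 unblinded attribution decides which non-local events are counted

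*Protocol*

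**What the plan says.** - **Endpoint.** Protocol 4.3.1 gives the primary endpoint as "All solicited and unsolicited local and general vaccine-linked adverse events (AEs) including clinically significant laboratory abnormalities". The primary evaluation criterion in Section 1 reads "Local and systemic solicited and unsolicited adverse events", with no condition on cause.
- **Blinding.** For groups 2 and 3, Section 7 states that "the investigators and the vaccinators will be un-blinded to the group allocations". Parents or carers are blinded, and so is the "field worker assessing adverse events in the 3 days immediately following vaccination will be blinded to the group allocation".
- **Who judges linkage.** Under 11.3.6 the investigator "will assess the relationship of the event to the administration of the vaccine". Section 11.3.8 adds: "The causal relationship between the AE and the product will first be evaluated by the investigator with the following scale". The word *first* suggests a second evaluation, but none is described, blinded or otherwise.
- **Local reactions.** Section 11.3.6 settles these by rule: "All local reactions will be considered causally related to the vaccination".
- **Severity.** Section 9.3 has field workers record reactions and class each solicited effect from absent to severe. Section 11.3.6 says: "The investigator will assess the severity of the solicited signs and symptoms using the key provided in Tables 4 and 5".
- **Why there are controls.** Sections 2.2 and 4.1 add rabies-vaccine controls in children because background illness is expected to be frequent, and to make the judgement of relatedness more objective.

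**The concern.** Sections 1 and 4.3.1 describe different counts. Under 4.3.1, a general, unsolicited or laboratory event enters the primary count only after someone has called it linked to vaccination, and in groups 2 and 3 that person knows which vaccine the child received. The same febrile illness could be counted after a malaria vaccine and dropped after rabies vaccine, or the reverse. The controls were added so that the comparison between arms would inform relatedness. With the filter in the endpoint, an unblinded opinion on relatedness shapes the comparison.

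The study is descriptive and has no formal test (12.1, 12.5), so the tabulated counts are themselves the primary result, and safety is the primary objective. Group 1 has no control arm, so the between-arm point concerns groups 2 and 3 only.

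**Working it through.** The plan states no event rate, attribution rate or error rate, so there is no figure of its own to reproduce. The check has two parts.

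**1. How much room the scale leaves (11.3.8)**

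- *No relationship* needs three conditions together: no temporal relationship, another aetiology, and no fit with the known response pattern.
- *Possible* needs any one of three conditions. A reasonable temporal relationship is enough, and no time window is given for it.
- *Probable* and *definite* need more conditions together.
- *Vaccine-linked* is mapped to none of these, so it is open whether a *possible* event counts.

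**2. What differential attribution does to the count**

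Inputs from the protocol: 6 children in each of six groups (12.2), so 4 × 6 = 24 receive malaria vaccine and 2 × 6 = 12 are controls.

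Assumptions, not in the protocol: p is the risk that a child has a general or unsolicited event, equal in both arms and taken as one event per child. q is the probability that the unblinded investigator calls the event linked.

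- Linked risk in an arm = p × q
- Spurious ratio = (p × q_vaccine) / (p × q_control) = q_vaccine / q_control; p cancels
- Spurious difference = p × (q_vaccine − q_control)

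Ratio: 0.20/0.10 = 2.0; reversed, 0.10/0.20 = 0.5; equal attribution gives 1.0.

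Difference, with p assumed between 0.3 and 0.8:

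| q vaccine v control | p = 0.3 | p = 0.5 | p = 0.8 |
|---|---|---|---|
| 0.5 v 0.5 | 0.00 | 0.00 | 0.00 |
| 0.6 v 0.4 | +0.06 | +0.10 | +0.16 |
| 0.7 v 0.3 | +0.12 | +0.20 | +0.32 |
| 0.8 v 0.2 | +0.18 | +0.30 | +0.48 |
| 0.4 v 0.6 | −0.06 | −0.10 | −0.16 |

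Example: p = 0.5 with q of 0.7 v 0.3 gives linked risks of 0.35 and 0.15. The expected counts are 24 × 0.35 = 8.4 of 24 and 12 × 0.15 = 1.8 of 12, although the true risks are the same.

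Local reactions have q = 1 in every arm by rule, so the filter leaves them unchanged. A count that ignores attribution has no q in it, so this source of bias disappears.

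**The case against.** A reader might infer that the control arms cannot support an unbiased safety comparison at all. The documents do not support that. Local reactions bypass the filter. Section 11.3.2 defines an adverse event whether or not it is thought related, 11.3.6 gathers details whatever the relationship, and 13.2 tabulates adverse events for description. A comparison free of attribution can be made from the planned data. During the first 72 hours, which 4.1 treats as the crucial period, carers and field workers are blinded. That protects early ascertainment, though not attribution.

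The size is also open to challenge. The attribution rates are assumed, and nothing shows that investigators would attribute differently by arm. If *linked* included *possible*, most early events in either arm might qualify, and the ratio would be near 1. Section 11.3.7 groups possible, probable and definite together for follow-up, which hints at that reading, but no passage applies it to the endpoint. This is why the missing mapping matters.

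The Section 1 entry is one line, does not say *all*, and could be shorthand for 4.3.1. It is still a different definition as written. An analysis plan could specify all-cause tables, but for the primary endpoint it would have to override one of the two.

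Nor would an all-event ratio necessarily be 1.0 in the absence of harm from the malaria vaccines. Clinic assessments on days 14, 63, 90 and 300 fall to the Principal Investigator (9.3), who is unblinded. The comparator itself causes mild systemic reactions in 5–40% of recipients (2.3.1). Stages 2a and 2b contain no control child (4.4.1, 8.5), so background is not fully concurrent.

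On severity, 9.3 and 11.3.6 can be read as complementary, with field workers grading at home and investigators at clinic visits. Several grades rest on millimetres, temperature or episode counts. This limb is the weaker one, but nothing says which grade is tabulated if both exist.

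**Conclusion.** The point holds as a defect in the endpoint definition. Section 4.3.1 applies a linkage filter that Section 1 lacks. In groups 2 and 3 unblinded investigators apply that filter to general, unsolicited and laboratory events, using a discretionary scale to which *vaccine-linked* is not mapped. The resulting bias can run in either direction, so it can hide a signal as well as produce one. Its size is unknown: the spurious ratio equals the ratio of attribution probabilities, and is 1.0 if these are equal. The figures of 2.0 and 0.5, and the table, show how the bias works under stated assumptions and do not predict what will happen. Neither the control arms nor the planned data collection is at fault in this respect. Because the primary endpoint is affected and the data for a cleaner summary will already exist, the wording should be corrected.

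**What to change.** - **Section 4.3.1.** Delete *vaccine-linked*. For groups 2 and 3, make the primary summary all solicited and unsolicited adverse events and clinically significant laboratory abnormalities, by arm and severity, regardless of causality, in line with Section 1.
- **Relatedness.** Report it as a secondary description, and state which categories in 11.3.8 count as linked.
- **Sections 9.3 and 11.3.6.** Reconcile them so that the blinded field worker's recorded grade is the one tabulated for days 1 to 3 after each vaccination. If an investigator regrades an event, keep that grade separately.

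**Cost.** The change is one of wording. It needs no new visits, samples or participants, and at most an extra field where a regrade is made. Background illness and rabies-vaccine reactions will enter the counts, so the comparison is malaria vaccine against rabies vaccine and not against background alone. Ascertainment after day 3 remains unblinded, and calling a laboratory abnormality clinically significant remains a judgement. The change therefore reduces the bias without removing it.
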